Number of investigators and study centers:

Approximately 15 to 20 sites in the United States, and other countries based on the pandemic situation.

Development phase:

Phase 2

Objectives:

The **primary objective** of this study is:

- To evaluate the efficacy of antroquinonol treatment of mild to moderate pneumonia due to COVID-19, as measured by the proportion of patients alive and free of respiratory failure (ie, no need for invasive mechanical ventilation, non-invasive ventilation, high-flow oxygen, or extracorporeal membrane oxygenation [ECMO]) on Day 14

The **secondary objectives** are:

- To further evaluate the efficacy of antroquinonol compared with placebo in this patient population as measured by:
 - World Health Organization (WHO) COVID-19 Clinical Improvement Ordinal Scale score on Days 7, 14, and 28
 - Duration of hospitalization up to Day 28
 - Virological clearance on Days 5, 14, and 28
 - Vital status (death) on Days 7, 14, and 28
 - Duration of intensive care unit (ICU) stay up to Day 28
 - Proportion of patients alive and free of respiratory failure on Days 7 and 28
 - COVID-19 symptoms on Days 7, 14, and 28
- To evaluate the safety of antroquinonol treatment in patients with mild to moderate pneumonia due to COVID-19.
- To assess the pharmacokinetics (PK) of antroquinonol in a subset of 20 patients (first 10 patients randomized to antroquinonol and first 10 patients to placebo)

The **exploratory objective** is to further evaluate efficacy via supportive analyses of:

- To further evaluate efficacy via supportive analyses of:
 - Subgroup analyses of selected covariates
 - Impact on efficacy of any new authorized treatments recommended as standard of care (SoC) for COVID-19 during the course of the study.

Methodology/study design:

This is a randomized, double-blind, placebo-controlled, Phase 2, proof of concept study in hospitalized patients with mild to moderate pneumonia due to COVID-19. Written informed consent must be obtained from all patients during screening (Days -2 to 0). Following completion of all screening assessments and meeting of eligibility criteria, patients will either receive antroquinonol or placebo for 14 days in combination with SoC therapy per local SoC policies.

A total of 174 patients are planned to be randomized in a 1:1 ratio to antroquinonol or placebo.

The study will consist of a sentinel cohort of 20 patients (10 patients randomized to antroquinonol and 10 patients to placebo), and an expansion cohort of 154 patients (77 patients in each treatment group). Enrollment will pause after the 20th patient in the sentinel cohort has been enrolled and started treatment, until the results of the interim analysis 1 are known. Once the 20th patient in the sentinel cohort has completed 14 days of treatment, an unblinded Data Monitoring Committee (DMC) will assess the safety, tolerability, efficacy, and PK of 100 mg twice daily (BID) antroquinonol in COVID-19 patients in the sentinel cohort (interim analysis 1). The DMC will issue a recommendation to enroll patients for the expansion cohort, or to stop the study depending on the safety and futility assessment. Once the 80th patient has been enrolled, and completed 14 days of treatment, the DMC will review the safety, tolerability, and efficacy data (interim analysis 2). Enrollment may be restricted at the 100th patient until the DMC has completed the assessment to prevent excessive enrollment. The DMC will continue to review safety and assess the risk/benefit profile on an ongoing basis. A DMC Charter, which includes detailed processes, will be prepared.

Patients will undergo assessment during hospitalization or could be discharged after start of study treatment any time after Day 2 if judged to be ready for discharge. If discharged, patients will then be requested to take study treatment at home (as prescribed) up to Day 14. End of Treatment assessments at Day 14 (+2 days) (at home or site visit) will be performed. A Day 5 (+/- 1 day) visit (at home or site visit) will be performed if the patient is discharged prior to Day 5. If the patient is discharged after completion of treatment and before the follow-up visit, he/she will be followed up on Day 28 (± 2 days) for study assessments (a telephone or telemedicine visit). Post discharge, assessments will be done by telephone or telemedicine, except for Day 5, Day 14, and Early Termination (ET) of Study Treatment. If the discharge, ET, or Early Withdrawal visit falls within the window of a scheduled Day visit, the assessments for the visits can be combined as one visit. On days of laboratory assessments, discharged patients will have a home visit. On days of no laboratory assessments, discharged patients will complete their assessments via telephone, telemedicine, or other means of remote communication. Additionally, patients will receive a diary to capture all doses after a discharge.

Number of patients:

A total of 174 patients are planned to be randomized into the study:

- 20 patients in the sentinel cohort (10 patients in each treatment group)
- 154 patients in the expansion cohort (77 patients in each treatment group).

This enrollment level ensures 80% power to demonstrate proof of concept efficacy with one-sided alpha of 0.2.

The sample size is based on the following assumptions:

- The randomized allocation ratio is 1:1 between the antroquinonol group and the placebo group
- The proportion of patients alive and free of respiratory failure is approximately 78% on placebo vs 89% on antroquinonol
- The following nonbinding rules will be considered by the DMC for futility, and the DMC will not make any recommendations to stop for early efficacy:
 - Interim analysis 1 (sentinel cohort): An odds ratio of 3.5 on the primary endpoint in favor of placebo.
 - Interim analysis 2: An odds ratio of 1.2 on the primary endpoint in favor of placebo. This analysis will be conducted on all data collected up to the 80th randomized patient completing 14 days of treatment. Enrollment may be restricted at the 100th patient until the DMC has completed the assessment to prevent excessive enrollment.

Diagnosis and criteria for inclusion and exclusion:

Patients must satisfy all of the following **inclusion** criteria at the Screening visit unless otherwise stated:

1. Willing and able to provide informed consent.
2. Male or female patients between 18 and 80 years of age.
3. Oxygen Saturation <94% in room air at screening.
4. Hospitalized with mild COVID-19 disease (not requiring oxygen therapy [WHO COVID-19 Clinical Improvement Ordinal Scale, score of 3] or requiring oxygen therapy by mask or nasal prong [WHO

COVID-19 Clinical Improvement Ordinal Scale, score of 4]). Requirement of oxygen therapy by mask with reservoir to treat severe COVID-19 pneumonia is not allowed for enrollment.

Note: Hospitalized patients can also include patients admitted to centers conditioned as hospitals to treat COVID-19 patients.

5. Chest x-ray or computerized tomography (CT) scan consistent with pneumonia.
6. Onset of COVID-19 symptoms within 2 weeks prior to randomization.
7. Severe Acute Respiratory Syndrome Coronavirus 2 (SARS-CoV-2) infection confirmed by a polymerase chain reaction (PCR) test, antigen, or any authorized commercial or public health assay (nasopharyngeal, oropharyngeal, or respiratory samples, not serology testing).
8. Male patients and female patients of childbearing potential must agree to use protocol-specified methods of contraception.
9. Female patients of childbearing potential must have a negative pregnancy test at Screening or pretreatment on Day 1.
10. Male patients must agree not to donate sperm from the first dose through 90 days after the last dose of study treatment; female patients of childbearing potential should refrain from donation of ova from Day 1 until 90 days after the last dose of study treatment.
11. Patient is, in the opinion of the investigator, willing and able to comply with the study treatment regimen and all other study requirements.

Patients will be excluded from the study if they satisfy any of the following **exclusion** criteria at the Screening visit unless otherwise stated:

1. Female patient is pregnant or breastfeeding.
2. Any patient's concomitant life-threatening condition, including but not limited to: requiring mechanical ventilation, acute respiratory distress syndrome, shock, or cardiac failure.
3. Evidence of multi-lobar consolidation pneumonia or cavities on chest x-ray or CT scan.
4. Severe COVID-19 disease as defined by the WHO COVID-19 Clinical Improvement Ordinal Scale, scores of 5 (non-invasive ventilation or high-flow oxygen), 6 (intubation and mechanical ventilation), or 7 (ventilation + additional organ support-pressors, renal replacement therapy, ECMO).
5. Medical history significant for the following pulmonary diseases: lung cancer, cystic fibrosis, empyema.
6. Respiratory rate >30 respirations per minute.
7. History of abuse of drugs or alcohol that could interfere with adherence to study requirements, as judged by the investigator.
8. Treatment with other drugs thought to possibly have activity against COVID-19 within 7 days prior to enrollment or concurrently. Note: remdesivir or other authorized treatments for COVID-19 is allowed if considered SoC, if started prior to randomization or during the study.
9. Use of *Antrodia camphorata* -containing products within 2 weeks prior to the first administration of study drug.
10. Use of other investigational drugs within 30 days of dosing, or plans to enroll in another clinical trial of an investigational agent while participating in the present study. Note: authorized COVID-19 vaccines are not considered investigational and are not exclusionary.
11. Clinically significant abnormal electrocardiogram (ECG) at Screening, as determined by the investigator.
12. Patient requires frequent or prolonged use of systemic corticosteroids (≥ 20 mg of prednisone/day or equivalent for >4 weeks) or other immunosuppressive drugs (eg, for organ transplantation or autoimmune conditions).
13. Abnormal laboratory values at Screening:
 - a. Estimated glomerular filtration rate <50 mL/min.
 - b. Alanine aminotransferase (ALT) or aspartate aminotransferase (AST) $>5 \times$ upper limit of normal (ULN), or ALT/AST $>3 \times$ ULN plus total bilirubin $>2 \times$ ULN.

- c. Total bilirubin $>1.5 \times$ ULN, unless the patient has known Gilbert's syndrome.
- d. Hemoglobin <9 g/dL for females or <11 g/dL for males.
- e. Absolute neutrophil count $<1,500/\text{mm}^3$.
- f. Thrombocytopenia (platelets count $<100 \times 10^9/\text{L}$).

14. Treatment with any antiviral drugs (except remdesivir or other authorized treatments for COVID-19), or with any drugs known to be strong inducers or inhibitors of cytochrome P450 isoform (CYP) 2C19, CYP3A4, CYP2C8, and CYP2E1 within 14 days or 5 half-lives prior to the start of study treatment. Drugs with a narrow therapeutic index that are substrates of 1A2, 2B6, 2C8, 2C9, 2C19, 3A, and 2D6 are also prohibited.

15. Inability to swallow oral medications or a gastrointestinal disorder with diarrhea (eg, Crohn's disease), malabsorption, or diarrhea of any etiology at baseline.

16. Any other clinically significant medical condition or laboratory abnormality that, in the opinion of the investigator, would jeopardize the safety of the patient or potentially impact patient compliance or the safety/efficacy observations in the study.

Test product, dose, and mode of administration:

Antroquinonol in a dose of 100 mg (1 capsule) administered BID orally, for 14 days.

Reference therapy, dose, and mode of administration:

Placebo (1 capsule) administered BID orally, for 14 days.

Duration of patient participation in study:

Total duration of patient participation is planned to be a maximum of 33 days.

The screening period is planned to be up to 3 days. The planned study treatment duration is 14 days.

Follow-up/EOS assessments will be performed on Day 28 (± 2 days).

Study populations:

Intention-to-treat (ITT): All randomized patients. Patients will be analyzed according to the treatment to which they were randomized.

modified ITT (mITT): All randomized patients who received at least 1 dose of study drug.

Per Protocol Set (PPS): All patients from the ITT set who have no important protocol deviations during the study. Patients with any important protocol deviations shall be excluded from the PPS prior to database lock.

Safety Set (SS): All patients who have received at least 1 dose of the study treatment. Patients will be analyzed according to the study treatment they actually received.

Pharmacokinetic Set (PKS): Patients in the sentinel cohort who have received at least 1 dose of the study treatment and have at least 1 evaluable plasma concentration without important protocol deviations or events thought to significantly affect the PK.

The ITT set will be the primary analysis population for efficacy and the mITT and PPS will be the supportive analysis populations for efficacy analysis. Safety endpoints will be analyzed using the SS. The PKS will be used for PK assessment.

Endpoints:

The **primary efficacy endpoint** is:

- The proportion of patients who are alive and free of respiratory failure (eg, no need for invasive mechanical ventilation, non-invasive ventilation, high-flow oxygen, or ECMO) on Day 14.

The **secondary efficacy endpoints** are:

- Clinical improvement score as measured by the WHO COVID-19 Clinical Improvement Ordinal Scale, as follows:
 - Time to 2-point improvement from baseline.
 - Supportive analysis, time to score 2 or lower.

- Supportive analysis, time to score 0.
- Duration of hospitalization (days) up to Day 28
- Virological clearance evaluated using PCR testing from nasopharyngeal or mid-turbinate samples on Days 5, 14, and 28:
 - Time to virological clearance, measured as study days from start of treatment to first negative SARS-CoV-2 PCR test
 - Rate of change in viral load will be evaluated depending on availability of quantitative assays.
- Vital status (death) on Days 7, 14, and 28
- Duration of ICU stay up to Day 28
- Proportion of patients alive and free of respiratory failure on Days 7 and 28
- COVID-19 symptoms on Days 7, 14, and 28. Assessment will evaluate: presence or absence of dry cough, dyspnea (shortness of breath/ difficulty in breathing), or chills/rigors, myalgia (muscle pain), headache, sore throat, and loss of taste or smell; other symptoms that could be related to COVID-19 will also be recorded.

The **exploratory efficacy endpoints** include:

- Age, sex, and remdesivir or other authorized treatments for COVID-19 use at baseline.
- Use of any new authorized treatments recommended as SoC for COVID-19 during the course of the study

The **safety endpoints** include the following variables:

- Adverse events (AEs)
- Standard safety laboratory tests (hematology, clinical chemistry, and urinalysis)
- Vital signs: respiratory rate, body temperature, blood pressure, pulse rate
- Complete physical examination: general appearance; head, eyes, ear/nose/throat, and neck; and lymphatic, cardiovascular, respiratory, gastrointestinal, musculoskeletal, neurological, and dermatological systems
- 12-lead ECG
- Chest imaging (x-ray or CT scan) findings

The **PK parameters** to be assessed from plasma samples (sentinel cohort only) are:

- Trough (predose) plasma concentration (C_{trough})
- Maximum plasma concentration (C_{max})
- Time to C_{max} (t_{max})

Area under the plasma concentration versus time curve (AUC) from time zero to the time of last quantifiable concentration ($AUC_{0\text{-last}}$), AUC within a dosing interval (AUC_{τ} , where $\tau = 12$ hours). On Day 14, if patients are still hospitalized, a predose and a 2-hours postdose sample will also be collected.

Statistical methods:

General Principles:

Continuous variables will be summarized by the standard descriptive statistics: number of patients (n), mean, standard deviation, median, minimum, and maximum. Frequency of patients or events and percentages will be summarized in categorical variables.

Results will be considered statistically significant at one-sided alpha of 0.025, and considered to indicate promising trend at one-sided alpha of 0.2.

Efficacy Analysis:

Primary Efficacy Analysis

The proportion of patients from each treatment group who are alive and free of respiratory failure on Day 14 will be compared using logistic regression. The p-value will be based on the Wald test. The primary model will be

stratified by remdesivir or other authorized treatments for COVID-19 use at baseline and by age at baseline (≤ 65 years vs > 65 years).

Secondary Efficacy Analysis

- Clinical improvement measured as a score on the WHO COVID-19 Clinical Improvement Ordinal Scale will be analyzed at each timepoint, adjusted for the clinical improvement score at baseline, age at baseline, and remdesivir or other authorized treatments for COVID-19 use at baseline, using an ordinal logistic regression on Days 7, 14, and 28. In addition, descriptive statistics will be provided for average score, and the proportion of patients at or below each score, at each timepoint. Time to 2-point improvement from baseline in WHO COVID-19 Clinical Improvement score, time to score of 2 or lower, and time to score of 0, will also be analyzed.
- The hazard ratio and its 95% confidence interval for time to event outcomes will be estimated by the Cox proportional hazard model, with patients censored at the time they are provided any antiviral therapy not prescribed at baseline, or on Day 28 if they have not yet recovered. Patients who die at any time will be considered not yet recovered by Day 28. Median time to 2-point improvement, time to score of 2 or lower, and time to score of 0 will be estimated by Kaplan-Meier (KM) method, and the KM curve will be provided. The p-value for comparison between groups will be obtained based on proportional hazards modeling stratified by the same covariates as the primary model.
- Duration of hospitalization and ICU stay up to Day 28 will be analyzed using normal regression, using the same covariates as for the primary endpoint. Patients who have died will be considered as continuing to require hospitalization or ICU up to Day 28 for the purposes of this analysis.
- Time to virological clearance, measured as study days from start of treatment to first negative SARS-CoV-2 PCR test, will be evaluated using similar statistical methods as clinical improvement. All patients who have died will be considered as not having cleared the virus by Day 28.
- Rate of change in viral load will be summarized descriptively and estimated using a Mixed Model for Repeated Measurements model. The model will include the treatment group, age, remdesivir or other authorized treatments for COVID-19 use at baseline, visit, and the interaction between visit and the treatment group as fixed factors, and will include the baseline value as a covariate.
- Proportion of patients with vital status of death in both groups on Days 7, 14, and 28 will be analyzed using logistic regression stratified by the same covariates as the primary model.
- Proportion of patients alive and free of respiratory failure on Days 7 and 28 will be compared using the same analysis as the primary endpoint.
- COVID-19 symptoms at screening and on Days 7, 14, and 28 will be summarized, and compared using logistic regression following the same method as the primary endpoint.

Exploratory Analyses

Subgroup analyses will be provided for the parameters of age, sex, and remdesivir or other authorized treatments for COVID-19 use at baseline. Investigation of the interaction between these parameters and the treatment effect will be provided. The impact on efficacy of any new authorized treatments recommended as SoC for COVID-19 during the course of the study will also be evaluated.

Safety Analysis:

Adverse events will be coded according to Medical Dictionary for Regulatory Activities version 23.0 dated 19 April 2020 (exclusively meant for COVID-19), or later.

The number and percentage of patients with treatment-emergent AEs (TEAEs), serious AEs (SAEs), TEAEs related to study treatment, SAEs related to study treatment, TEAEs leading to treatment discontinuation, and TEAEs leading to death will be summarized by system organ class (SOC), preferred term (PT), and treatment group. In addition, the severity of TEAEs and relationship to study treatment will be summarized by SOC, PT, and treatment group.

Test values and change from baseline will be summarized descriptively for specific laboratory test results, vital signs, and complete physical examination, ECG, and chest imaging (x-ray or CT scan) findings. Where applicable, shift tabulations by treatment group will be presented.

Pharmacokinetic Analysis:

Descriptive statistics will be provided for antroquinonol plasma concentrations at prespecified timepoints and derived PK parameters.

TABLE OF CONTENTS

TITLE PAGE.....	1
SPONSOR APPROVAL	2
INVESTIGATOR AGREEMENT	3
SYNOPSIS	4
TABLE OF CONTENTS	11
LIST OF TABLES AND FIGURES	13
LIST OF ABBREVIATIONS.....	14
1. INTRODUCTION.....	16
1.1. Study Rationale	16
1.2. Background.....	16
1.2.1. Investigational product	17
1.2.2. Nonclinical and preclinical data	17
1.2.3. Clinical data.....	17
1.3. Benefit-risk Assessment	19
2. OBJECTIVES AND ENDPOINTS.....	20
2.1. Objectives.....	20
2.2. Endpoints.....	20
3. INVESTIGATION PLAN	23
3.1. Overall study design and plan description.....	23
3.2. Discussion of study design, including the choice of control groups.....	24
3.3. End of study definition	25
3.4. Selection of doses in the study.....	25
4. SELECTION OF STUDY POPULATION	27
4.1. Inclusion Criteria	27
4.2. Exclusion Criteria.....	27
4.3. Disease Diagnostic Criteria	29
4.4. Discontinuation Criteria	29
4.4.1. Screen failures	29
4.4.2. Hepatic injury or renal impairment.....	29
4.4.3. Discontinuation of study treatment.....	30
4.4.4. Study withdrawal	31

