3.4. Selection of doses in the study

Antroquinonol is already in clinical development, albeit in cancer patients, and shown to be well tolerated. Levels have included oral single doses of 50-600 mg and 200 mg BID (BID use has occurred due to a short plasma half-life of 1.30 to 4.33 hours). For the proposed clinical work, a starting dose of 100mg (given BID due to short half-life) is proposed based around anti-inflammatory activity in mouse efficacy work and the rat no-observed-adverse-effect-level (NOAEL) from toxicology testing. In the former, a 15-50 mg/kg/12.3 body surface factor was calculated to correspond to a 1.22-4.07 mg/kg human equivalent dose, or 85-285 mg for a 70 kg person. Therefore, a dose of 100 mg BID is within the animal efficacy range. The proposed dose is also supported by the rat study NOAEL on a mg/m² basis with an approximate 2-fold safety

margin [NOAEL in rat (30 mg/kg) x 6 (to convert dose in mg/kg to dose in mg/m²) = 180 mg/m² vs human 200 mg daily dose = 2.9 mg/kg x 37 (dose in mg/kg to dose in mg/m²) which converts to 108 mg/m² for a 70 kg person].

The safety of antroquinonol in patients with mild to moderate pneumonia caused by COVID-19 will be confirmed at 100 mg BID in the sentinel and expansion cohorts, which is within the animal efficacy range.

Treatment duration was selected based on the clinical presentation of the disease. Patients with COVID-19 experience systemic symptoms for approximately 7 to 10 days, and patients with disease progression but without ventilator use are typically hospitalized for 5 to 7 days. In a subset of patients, a cytokine storm can emerge resulting in complications. A treatment duration of 14 days should be adequate to treat the infection and prevent the immune response complications.

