7.1.2. Secondary efficacy endpoints

7.1.2.1. *Clinical improvement*

The WHO COVID-19 Clinical Improvement Ordinal Scale will be used to assess a clinical improvement score on Days 7, 14, and 28. See [Appendix 7](#) for details on the scale.

7.1.2.2. *Duration of hospitalization*

The number of days a patient has been hospitalized prior to study entry will be recorded in the eCRF.

Duration of hospitalization is the total number of days the patient is hospitalized during their participation in the study, up to Day 28.

7.1.2.3. *Virological clearance*

PCR testing for SARS-CoV-2 will be performed at a local or central laboratory at screening. Results of a confirmatory COVID-19 test already done as SoC can be used to determine eligibility. All subsequent tests (Day 1 and later) will be performed by a central laboratory. The PCR testing for SARS-CoV-2 will be collected during hospitalization as noted in the Schedule of Assessments ([Appendix 5](#)) and evaluated by the central laboratory.

Virological clearance will be measured by:

- **Time to viral clearance:** This endpoint will measure the time (days) to the first negative test for COVID-19.
- **Rate of change in viral load:** if quantitative PCR results are performed, the level of virus will be measured over time (days).

7.1.2.4. *Vital status*

Patient mortality will be recorded up to Day 28 and summarized in the analysis on Days 7, 14, and 28. Every effort will be made to ascertain vital status in all randomized patients (eg, with a vital records search) up to Day 28.

7.1.2.5. *Duration of ICU stay*

Duration of ICU stay is defined as the total number of days the patient is managed in the ICU during their participation in the study, up to Day 28. The date of the start and stop of the ICU stay must be recorded in the eCRF; no daily assessment is needed.

7.1.2.6. *Respiratory failure free*

The proportion of patients alive and respiratory failure free will be evaluated on Days 7 and 28. Respiratory failure is defined as the need for invasive mechanical ventilation, non-invasive ventilation, high-flow oxygen, or ECMO. The date of the start of the respiratory intervention must be recorded in the eCRF; no daily assessment is needed.

7.1.2.7. *COVID-19 symptoms*

COVID-19 symptoms assessment at the times indicated in the Schedule of Assessments in [Appendix 5](#) will evaluate: presence or absence of dry cough, dyspnea (shortness of breath/

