8.3. General Considerations

Continuous variables will be summarized by the standard descriptive statistics: number of patients (n), mean, standard deviation, median, minimum, and maximum. Frequency of patients or events and percentages will be summarized in categorical variables.

Missing values on clinical improvement score will be imputed using Last Observation Carried Forward for a maximum of 1 day at Day 7, 2 days at Day 14, and 4 days at Day 28. For

respiratory failure status, where a patient has died, their status will not be considered missing but will be treated as an observation at each timepoint.

Unless otherwise stated, all regression models will be adjusted for age and remdesivir or other authorized treatments for COVID-19 use at baseline.

Results will be considered statistically significant at one-sided alpha of 0.025, and considered to indicate promising trend at one-sided alpha of 0.2.

Additional information is available in the statistical analysis plan (SAP).

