### 7.6.2.2 Duration of Hospitalization and ICU Stay

Duration in days of hospitalization and ICU stay up to Day 28 will be summarized descriptively and analyzed using normal regression, with treatment, remdesivir or other authorized treatments for COVID-19 use at baseline (yes vs no) and age at baseline ( $> 65$  years vs  $\leq 65$  years) as covariates. P-values for treatment effect will be provided using the Student's t-test.

Notes: 1) Only hospitalization or ICU stay days on or after the date of first dose of study treatment and up to Day 28 will be used in the calculation of duration of hospitalization or ICU stay, respectively; 2) Patients who have died or with unknown discharge date will be considered as continuing to require hospitalization or ICU stay up to Day 28.

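### Hospital days before study entry are recorded but enter no model or baseline table, although duration of hospitalization counts only the stay from first dose; the regression may give up a little precision

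*Protocol*

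**What the plan says.** Protocol 7.1.2.2 defines the endpoint: "Duration of hospitalization is the total number of days the patient is hospitalized during their participation in the study, up to Day 28". SAP 7.6.2.2 narrows it: "Only hospitalization or ICU stay days on or after the date of first dose of study treatment and up to Day 28 will be used". Days before entry therefore never count towards the outcome.

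The same protocol section collects those days: "The number of days a patient has been hospitalized prior to study entry will be recorded in the eCRF". The footnote on efficacy assessments repeats this in the schedules of both documents.

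The model is given in the protocol synopsis and in 8.4.2: "Duration of hospitalization and ICU stay up to Day 28 will be analyzed using normal regression, using the same covariates as for the primary endpoint". SAP 7.6.2.2 spells it out: "analyzed using normal regression, with treatment, remdesivir or other authorized treatments for COVID-19 use at baseline (yes vs no) and age at baseline", with age split at 65 years. Protocol 8.3 sets the default: "Unless otherwise stated, all regression models will be adjusted for age and remdesivir or other authorized treatments for COVID-19 use at baseline". The same two factors stratify randomization (protocol 5.3).

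Pre-entry hospital days are not among the baseline variables in SAP 7.4 and 7.5, nor among the subgroups in SAP 7.6.3. At most they would reach the by-patient listings described in SAP 7.1.

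**The concern.** The outcome is a residual stay, measured from a starting point that can differ between patients. Two patients with the same disease course contribute different values if one is randomized on the day of admission and the other several days later. How far into the admission each patient was at entry is therefore an obvious candidate covariate. It is already collected, and in the section that defines this endpoint.

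Leaving it out has two consequences. Any variation in residual stay that pre-entry days could explain stays in the error term. A chance difference between arms in pre-entry days is neither adjusted for nor shown to the reader, since no table reports it by arm. Only one secondary endpoint is at stake.

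**Working it through.** **No plan figure to reproduce.** Neither document gives a standard deviation, effect size or power for duration of hospitalization. The stated 80% power belongs to the primary endpoint and does not bear on this point.

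**Step 1: cost and gain of one extra covariate.** The planned model has four parameters (intercept, treatment, therapy, age group), so with 174 patients there are 170 residual degrees of freedom. Let r be the partial correlation of pre-entry days with in-study days, given the other terms. Adding the covariate multiplies the variance of the treatment estimate by approximately

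(1 − r²) × (1 + 1/(170 − 2)) = (1 − r²) × 1.006.

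The equivalent number of patients is 174 divided by this ratio.

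| r (assumed) | Variance ratio | Equivalent N |
|---|---|---|
| 0 | 1.006 | 173 |
| 0.1 | 0.996 | 175 |
| 0.2 | 0.966 | 180 |
| 0.3 | 0.915 | 190 |
| 0.4 | 0.845 | 206 |
| 0.5 | 0.755 | 231 |

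Break-even is where (1 − r²) × (169/168) = 1, so r² = 1/169 and |r| = 1/13, about 0.08. Below that, the extra term costs slightly more than it returns, and never more than about 0.6% of variance on average.

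**Step 2: what r² might be.** The documents do not give r, so it was simulated. All of the following are assumptions:
- total stay Weibull with mean 6, 10 or 14 days;
- pre-entry days uniform on 0 to 4 or 0 to 7, with patients still in hospital at entry;
- residual stay rounded up and capped at 28, with random deaths set to 28 as SAP 7.6.2.2 requires.

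| Assumed setting | Variance explained (r²) |
|---|---|
| Identical patients, constant discharge rate (shape 1) | 0% |
| Identical patients, shape 2, 3% deaths | 2% to 5% |
| Identical patients, shape 2, 10% deaths | 1% to 3% |
| Identical patients, shapes 1 to 3, 3% deaths | up to about 12% (shape 3, mean 10 days, pre-entry 0 to 7) |
| Identical patients, shapes 1 to 3, 10% deaths | up to about 6% to 7% |
| Expected stay varies between patients (lognormal SD 0.5, shapes 0.8 to 3), 3% deaths | up to about 3% |
| Same, 10% deaths | up to about 2% |
| Expected stay varies more (lognormal SD 0.8) | up to about 2%; the largest correlation is positive |

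With identical patients and a rising discharge rate, the correlation is negative: more days already spent means fewer left. Once expected stay varies between patients, those still in hospital after several days are increasingly the slow recoverers. That offsets the first effect and can reverse the sign.

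**Step 3: put the two together.**
- r² = 0.03: ratio 0.97 × 1.006 = 0.976; 174/0.976 is about 178, so about 4 extra patients.
- r² = 0.12: ratio 0.88 × 1.006 = 0.885; 174/0.885 is about 197, so about 23 extra patients.
- r² = 0: ratio 1.006, a loss of about 1 patient.

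**The case against.** The strongest reply is that this is a preference, not an error. The plan applies one rule to its regressions, adjustment for the two randomization factors, and using it for a secondary endpoint is coherent. That stands: the documents do not contradict each other here, and no bias arises, because randomization balances pre-entry days in expectation. It does not make the omission a considered choice, however. The protocol's default is open to exceptions. The plan already makes them where a baseline quantity is tied to the outcome: the ordinal model takes the baseline WHO score, and the viral-load model takes baseline viral load.

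A reader might infer that precision is definitely being lost, perhaps to the value of some 24 patients (174 × (1/0.88 − 1), before the cost of the extra term). The documents do not support that. The figure comes from one corner of the assumed range: identical patients, a steeply rising discharge rate and 3% deaths. The gain may be nil or very slightly negative.

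It is also tempting to argue from the protocol's remark in section 3.4 that "patients with disease progression but without ventilator use are typically hospitalized for 5 to 7 days": a patient four days in would then have little stay left. That treats a typical figure as a fixed total and ignores the fact that quick recoverers have already gone home. The remark also describes only one group of patients and is there to justify treatment duration.

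Three further limits are fair. Setting deaths and unknown discharge dates to Day 28 dilutes any correlation. The only mortality figure in the protocol, 21% in a cited general hospitalized cohort (section 8.1), is probably high for this trial; at 21% deaths, mean stay 6 days and identical patients, r² is at most about 1%. The symptom-onset window of two weeks probably restricts the spread of pre-entry days. Finally, the listings may show the variable, but a listing by patient is not a comparison by arm.

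**Conclusion.** The point holds as a minor, optional improvement. A baseline variable directly related to a residual-stay endpoint is collected and then used in no model or baseline summary. The planned analysis remains valid and unbiased.

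The likely precision gain is small: 0% to about 3% of variance explained if expected stay varies between patients, worth up to about 4 patients in 174. The sign of the association is uncertain, but the regression estimates it, so the case for the covariate does not depend on it. The cost if the variable is not prognostic is about 0.6% of variance. All the sizes rest on assumed stay distributions, death rates and pre-entry spreads, since the documents supply none.

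The case for the baseline table does not depend on the correlation: without it, a reader cannot tell whether the arms entered at a similar point in their admission. The argument does not carry over directly to ICU stay, which the same sentence covers. The primary analysis and the sample size of 174 are untouched.

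**What to change.** Before unblinding:

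1. In SAP 7.6.2.2 and protocol 8.4.2 (and the matching synopsis text), add the number of days hospitalized before study entry, as a numeric covariate, to the duration-of-hospitalization model only. Leave the ICU-stay model as it is.
2. In SAP 7.5, summarize the same variable by treatment group and overall.
3. Optionally, add the baseline WHO score to the same model. SAP 7.6.2.1 already uses it as a numeric covariate in the ordinal regression, and it is missing here too.

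If only the SAP is changed, its section 8, which now reports no departures from the protocol's methods, must record the addition.

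The cost is one model term (two with the WHO score) and one set of rows in a baseline table. No new data, no patient burden and no change in sample size are needed.
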